10.1. Sample Size Determination

10.1.1. Part A

The sample size of approximately 25 randomized participants in each of the 4 treatment groups is not based on statistical power consideration due to the lack of information of AGN-241751 for the variability of change from baseline to 1 day after first dose in MADRS total score.

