4.0 INTRODUCTION

This statistical analysis plan (SAP) provides a more technical and detailed elaboration of the statistical analyses of the efficacy and safety data for part A as outlined and/or specified in the final protocol of Study 3125-104-002 and the most recent protocol amendment (Amendment 1 dated 05 March 2019; Amendment 2 dated 03 May 2019). Specifications of tables, figures, and data listings are contained in a separate document.

Part A of study 3125-104-002 is a Phase 1b, multicenter, randomized, double-blind, placebo-controlled, parallel-group (4 arms), weekly and once daily dose, 2-week study of AGN241751 in participants with major depressive disorder (MDD). The study will include a total of 7 visits and will be approximately 5 weeks in duration:

- Up to 2-week screening period
- 2-week double-blind treatment period
- 1-week safety follow-up period

After providing written consent, participants will enter a screening period of up to 14 days. Screening procedures may be conducted on up to 2 separate dates where necessary to accommodate participant and site schedule; however, every effort should be made to conduct all procedures as early as possible in the screening period, including the rater-administered montgomery- asberg depression rating scale (MADRS). Participants meeting the eligibility criteria at the end of Visit 2 (Day 1 of the randomized inpatient treatment) will be assigned a treatment and enter the double-blind treatment period.

Approximately 100 participants are planned for enrollment in the double-blind treatment period (25 participants each in the AGN-241751 and placebo groups). Participants will be randomized in a ratio of 1:1:1:1 to 1 of 4 treatment groups: 3 mg, 10 mg, and 25 mg dose AGN-241751 and placebo. All participants will be randomized to receive active treatment or placebo (Day 1, and Days 8 to 15) and placebo alone (Days 2 through 7).

[figure not shown]

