10.0 EFFICACY ANALYSES

The efficacy analyses will be based on the mITT Population. Baseline for efficacy is defined as the last nonmissing efficacy assessment before the first dose of study treatment. All statistical tests will be 2-sided hypothesis tests performed at the 5% level of significance. All confidence intervals will be 2-sided 95% confidence intervals, unless stated otherwise.

For efficacy analyses in which study center is a factor, a small center will be defined as a center with fewer than 2 participants for at least 1 treatment group in the mITT Population. Small centers will be pooled to form pseudo-centers so that each treatment group includes at least 2 mITT participants within the center. Pooling will be done within each country using the following algorithm:

1. Based on the number of mITT participants, small centers will be ordered from the largest to the smallest, and centers of the same size will be ordered from the largest center number to the smallest center number.
2. The pooling process starts with the largest small center from the top, which will be pooled with the smallest from the bottom until a non-small center is formed.
3. The process will be repeated using the small centers left out after the first pass.

If any centers are left out at the end of the process, they will be pooled with the smallest pseudo-center. If there is more than 1 smallest pseudo-center, the pseudo-center with the smallest center number will be selected. In case that the pseudo center formed by pooling all small centers is still a small center, it will be pooled with the smallest non-small center. If there is more than 1 smallest non-small center, the one with the smallest center number will be selected.

The pseudo-centers will be used for all efficacy analyses when the model is adjusted for study center.

The rater-administered MADRS will be used for the efficacy analyses.

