10.3 ADDITIONAL EFFICACY PARAMETERS

Additional efficacy parameters are as follows:

- Change from baseline in Clinical Global Impressions-Severity (CGI-S) at Day 2 (1 day after first dose), Day 8, Day 9 and Day 15
- MADRS responder status at Day 2 (1 day after first dose), Day 8, Day 9, Day 15 and Day 22
- CGI-S responder status at Day 2 (1 day after first dose), Day 8, Day 9 and Day 15
- MADRS remitter status at Day 2 (1 day after first dose), Day 8, Day 9, Day 15 and Day 22
- Time to first response
- Time to first remission

Analysis of change from baseline in CGI-S score will be performed using a similar MMRM to that used for the key secondary parameter. Multiple comparison procedure will not be applied to the above additional efficacy parameters.

Plots of fitted (least squares) mean values and their standard errors based on the MMRM model for the change from baseline in MADRS total score and in CGI-S score, respectively, will be presented by treatment group and by visit.

CGI-S responder is defined as participants achieving a score of ≤ 2 on the CGI-S of Illness scale.

During the randomized treatment period, 2 types of events for MADRS total score will be defined based on the following criteria:

- Responder: $\geq 50\%$ reduction from baseline MADRS total score
- Remitter: MADRS total score ≤ 10

Rates of responders and remitters will be reported by treatment group for each timepoint (Days 2, 8, 9, 15, and 22 after first dose of randomized treatment). A logistic regression model with LOCF imputation will be used to model the probability of a response or the probability of a remission as a function of a treatment group and baseline MADRS or CGI-S total score. The LOCF approach will be used to impute missing postbaseline values, provided that at least 1 postbaseline assessment is available. Missing values between the baseline and the first nonmissing postbaseline will be imputed with the baseline value. If all the postbaseline values are missing, the baseline value will not be carried forward. Only the total score of a parameter will be imputed using the LOCF approach; individual item scores will not be carried forward. Bar charts for the rates of responders and remitters in MADRS total score will be presented by treatment group and by study day.

Descriptive statistics for the first three additional endpoints and their associated statistical testing results from the MMRM models and logistic regression will be respectively presented by visit.

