14.0 DETERMINATION OF SAMPLE SIZE

The sample size of approximately 25 randomized participants in each of the 4 treatment groups is not based on statistical power consideration due to the lack of information of AGN-241751 for the variability of change from baseline to 1 day after first dose in MADRS total score.

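### SAP 10.3 plans by-visit logistic regression with about 25 per arm but has no rule for an arm with no events; at low event rates, most plausibly Day 2 remission and CGI-S response, the odds ratio would not be finite

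*SAP*

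**What the plan says.** SAP 10.3 (Additional Efficacy Parameters) says a logistic regression with LOCF is "used to model the probability of a response or the probability of a remission as a function of a treatment group and baseline MADRS" (alternatively CGI-S) total score. Three binary endpoints are involved:

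- MADRS response, a reduction of at least 50% from baseline, at Days 2, 8, 9, 15 and 22.
- MADRS remission ("Remitter: MADRS total score" of 10 or less), listed as "MADRS remitter status at Day 2 (1 day after first dose), Day 8, Day 9, Day 15 and Day 22".
- CGI-S response at Days 2, 8, 9 and 15 ("CGI-S responder is defined as participants achieving a score of" 2 or less).

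Test results are to be presented by visit for the first three items on the section's list. Those include MADRS response and CGI-S response; MADRS remission is fourth.

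Protocol 10.1.1 plans "approximately 25 randomized participants in each of the 4 treatment groups", and SAP 14.0 confirms that this size has no power basis. SAP 10.0 adds: "All statistical tests will be 2-sided hypothesis tests performed at the 5% level of significance".

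Neither SAP 10.3 nor Protocol 10.3.1.3.1 names the estimation method or the test statistic, or says what happens when an arm has no events. SAP 15.0 names only the SAS version. For the primary MMRM, by contrast, SAP 10.1 gives an ordered list of fallback covariance structures in case the model does not converge.

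**The concern.** The event definitions are demanding relative to the entry criteria, and the first analysis comes one day after a single dose. Protocol 6.1 requires a MADRS score of at least 26 and a CGI-S score of at least 4, so some of these events may be rare at Day 2. With about 25 per arm, a rare event can easily leave an arm with none.

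In that case a standard maximum-likelihood fit has quasi-complete separation. The log odds ratio for the empty arm drifts without limit, its standard error explodes, and the Wald p-value tends to 1 whatever the data show. If no remedy is written down, one has to be chosen after the problem appears, possibly with treatment codes known, and the available remedies can give quite different p-values on the same data.

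**Working it through.** **Inputs from the documents.** Four arms at 1:1:1:1, about 25 each (SAP 4.0 and 14.0). Entry MADRS at least 26 and CGI-S at least 4 (Protocol 6.1). Event thresholds as in SAP 10.3. Remission therefore needs a fall of at least 26 − 10 = 16 points (16/26 = 62%), and CGI-S response a fall of at least 4 − 2 = 2 categories. Under the LOCF rule in SAP 10.3, a participant with a missing early visit but a later assessment takes the baseline value, hence counts as a non-event; this slightly raises the chance of an empty arm.

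**Inputs not in the documents.** No event rates are given, so there is no planned figure to reproduce. I assume a common rate p in all arms and show a range.

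**Chance of an empty arm.** With 25 per arm:

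- one given arm: q = (1 − p)^25
- at least one arm of a given dose-placebo pair: 1 − (1 − q)^2
- at least one of four arms: 1 − (1 − q)^4

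| Assumed rate p | One given arm | Given pair | Any of four |
|---|---|---|---|
| 2% | 60% | 84% | 98% |
| 5% | 28% | 48% | 73% |
| 8% | 12% | 23% | 41% |
| 10% | 7.2% | 14% | 26% |
| 15% | 1.7% | 3.4% | 6.7% |
| 20% | 0.4% | 0.8% | 1.5% |

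For example, at 5%: q = 0.95^25 = 0.277, and 1 − (1 − 0.277)^4 = 0.727. At least one arm is more likely than not to be empty below a rate of about 7.1%; the chance drops under 10% above about 13.6%. With 20 analysed per arm, the any-of-four figures are 83% at 5%, 40% at 10% and 4.5% at 20%.

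**Which endpoints could have such rates?** As a rough guide only, I assumed a normal model: baseline mean 32, SD 4, truncated to scores of 26 to 50, with SD of change 8.

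| Assumed mean fall | Response rate (any arm empty) | Remission rate (any arm empty) |
|---|---|---|
| 6 points | 10.5% (23%) | 2.8% (93%) |
| 10 points | 22% (0.7%) | 7.5% (46%) |
| 15 points | 44% (about 0%) | 19.5% (2%) |

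Remission is far more exposed than response, and exposure fades as improvement accumulates. CGI-S response was not modelled; its exposure is inferred from the two-category fall it needs.

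**What an empty arm does to the fit.** Both examples use invented counts, simulated baselines, three treatment indicators and the baseline score.

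- *Placebo empty* (0/25 against 3, 4 and 6/25). Under maximum likelihood every log odds ratio grows by about 1 per iteration. For the 6/25 arm it goes from about 8 at iteration 8 to about 25 at iteration 25, while the SE goes from about 20 to about 98,000 and the Wald p from 0.69 to 1.00. Firth estimation gives finite odds ratios of 8.0, 10.6 and 17.2 (SE of the log about 1.5). For 6/25 against 0/25, the p-values are 1.00 (Wald), 0.002 (ordinary likelihood ratio), 0.007 (penalised likelihood ratio) and 0.022 (Fisher exact).
- *One active arm empty* (placebo 2/25; active 0, 3 and 6/25). Only the empty arm's log odds ratio diverges, to −23.8 by iteration 25. The other two stay at 0.40 and 1.39. Firth gives 0.34 and 1.23 for those two, which shows the shrinkage: odds ratios of 1.41 and 3.41 instead of exp(0.40) = 1.49 and exp(1.39) = 4.01.

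**The case against.** A reader might infer that the planned tests will routinely fail at the early visits. The documents do not support that. They give no event rates, and at 15% or more the chance of any empty arm is under 7%, so MADRS response may well be unaffected, especially after Day 2. Protocol 5.4 also notes that placebo groups in depression improve substantially and variably, although it does not say so of Day 2. A drug effect would make events commoner on active treatment, but it would not protect the placebo arm, whose loss is the more damaging case.

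A reader might also infer that the SAP prescribes maximum likelihood with Wald tests. It does not; these are ordinary defaults. A likelihood-ratio test from the same fit remains usable. What stands is that the choice is open and that it matters: the p-values above run from 0.002 to 1.00 on one set of counts.

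Nor would a whole visit's results necessarily be lost. Unless placebo is the empty arm, only the empty arm's contrast fails. Remission, the most exposed endpoint, is outside the sentence committing to test results, although the model sentence covers it; CGI-S response is inside both.

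Finally, SAP 10.3 already reports responder and remitter rates by group and timepoint, and its log-rank tests for MADRS response and remission still work when one arm has no events. Those tests are not by visit and do not cover CGI-S, so they soften the gap without closing it.

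**Conclusion.** The point holds as a minor one. The SAP fits by-visit logistic models to small arms without naming an estimator, a test or a rule for an arm with no events. The size depends on assumed rates: an empty arm among the four is more likely than not below about 7%, and unlikely (under 7%) at 15% or more. Rates low enough to matter are plausible mainly at Day 2, for remission and for CGI-S of 2 or less. The calculation assumes a common rate across arms and 25 analysed per arm.

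It would be wrong to read this as a threat to the trial's main conclusions. These are additional endpoints without multiplicity control, and the primary Day 2 and key secondary analyses use an MMRM on the continuous MADRS score, which an empty event cell does not touch. It is worth acting on because the remedy is cheap and works at any rate, provided at least one participant has an event.

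**What to change.** Add to SAP 10.3, before unblinding, that all responder and remitter models use Firth-penalised logistic regression with the same covariates, profile-likelihood confidence intervals and penalised likelihood-ratio tests. Where no participant in any arm has an event at a visit, report proportions only: Firth cannot give a useful comparison there, and at a 2% rate this has probability 0.98^100 = 13%. Add exact confidence intervals to the rates already planned.

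The cost is a short addition to the SAP and one option in the SAS procedure. The downside is slight shrinkage of the odds ratios, of the order shown in the second example. Likelihood-ratio or exact tests would also serve for testing; the essential step is to fix the choice in advance.

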- It is expected that participants in the double-blind treatment period will remain inpatient during the 1st week (Visit 2 to Visit 10/Discharge).
- During the inpatient treatment period, participants will have 7 visits (Visits 3 to 9); each visit will occur daily with no visit windows.
- At Visit 3 (Day 1) during the predose evaluation period, if there is a significant change (worsening or improvement in depressive symptoms) from the baseline Visit 2 (Day -1) MADRS based on the judgment of the PI, a MADRS assessment should be performed prior to the 1st dose of study medication.
- Participants will be discharged at Visit 10 (Day 8) after all predose assessments, morning dosing, and 4-hour postdose assessments are completed.
- During the inpatient treatment period, predose assessments will be performed prior to morning dosing at all inpatient visits (Visit 3 through Visit 10). Postdose assessments will be performed, as follows:
 - Visit 3 to Visit 6: 1, 2, 4, 8, and 12 hours after the morning dose (\pm 20 minutes)
 - Visit 7 to Visit 9: 4, 8, and 12 hours after the morning dose (\pm 20 minutes)
 - Visit 10: 4 hours after the morning dose (\pm 20 minutes)
- Within each timepoint, multiple assessments will be performed, as follows:
 - Assessments should be performed within \pm 20 minutes of each other
 - All psychiatric assessments (Likert Patient Depressive Symptom Scales, CSSR-S, MADRS, and CGI-S) are to be completed first prior to any other assessments (ie, qEEG, ERP) within the timepoint.
 - Participants are required to not use any nicotine substances 1 hour prior to administration of the HVLT-R.
- The afternoon dose of study medication is to be administered 8 hours (\pm 1 hour) after the morning dose.

[figure not shown]
Week 2 Outpatient Double-Blind Treatment Period

- During the outpatient treatment period, there will be 2 visits conducted every 3 days (Visit 11 [Day 11] and Visit 12 [Day 14/ET]). If necessary, these study visits may be conducted up to 1 day before or after the scheduled visit day.
- All participants who receive study medication should complete Visit 12 (Day 14/ET)
- At Visit 10 (Day 8) prior to discharge, the participant will be dispensed Bottle 2 of study medication (refer to Section 7.1.2 for dosing instruction). Participants will be instructed to bring the study medication bottle to Visit 11 for the site staff to confirm dosing compliance

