Participants will have 7 study visits during the study. The first 6 visits will occur in the following pattern: the Screening Visit (Visit 1; up to Day -14); at Visit 2 (Day 1 of the randomized inpatient treatment); at Visit 3 (1 day following the inpatient treatment day); at Visit 4 (7 days following the first inpatient treatment day, which is the second inpatient treatment day); at Visit 5 (1 day following the second inpatient treatment day); and at Visit 6 (7 days following the second inpatient treatment day). If necessary, study visits may be conducted up to 2 days before or after the scheduled visits with the exception of visits that are 1 day apart (ie, Visits 2 and 3 must be conducted 1 day apart; and Visits 4 and 5 must be conducted 1 day apart). Participants will enter a 1-week safety follow-up period and return for Visit 7. Participants who prematurely discontinue from the study before completing the double-blind treatment should enter the 1-week safety follow-up period. Additional follow-up visits may be scheduled within 30 days, if necessary for safety reasons.

Figure 4-1

Study Design Diagram

FU = follow-up; IP = investigational product.

All treatments will be presented to participants as oral once daily dosing throughout the study.

At Visit 2 (Day 1 of the randomized inpatient treatment), all participants will be randomized to receive the first treatment, followed by blinded placebo on Days 2 through 7.

Starting at Visit 4 (Day 8), participants will then start 7 consecutive days of double blinded randomized treatment, administered once daily through Day 15.

The schedule of activities for Study 3125-104-002 is presented in [Table 4-1](#). The double-blind treatment period starts with the first dose of study (Day 1) treatment and ends with the last dosing day (Day 15).

Table 4-1 Schedule of Activities (SoA)							
		Double-blind Treatment Period					Safety Follow-up Period
Visit	Screening (1)	2	3	4	5	6/ET^a	7
Study Day	up to -14 days	1	2	8	9	15	22
Informed consent	x						
Medical (surgical, neurologic) and psychiatric histories	x						
Prior medication history	x						
Inclusion/exclusion	x	x					
Randomization assessment		x					
Clinical laboratory determinations ^b	x	x				x	
Urine drug screen	x					x	
Serum pregnancy test	x					x	
Pharmacogenomics consent and sample ^c				x			
Vital signs ^d	x	x	x	x	x	x	x
ECG	x					x	
Physical examination	x					x	
SCID	x						
MADRS	x	x	x	x	x	x	x
CGI-S	x	x	x	x	x	x	
BPRS+	x		x	x	x	x	
CADSS	x		x	x	x	x	

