The time to onset of first event (i.e. first response or first remission) is defined as the number of days from the first randomized dosing to the first event. The time to onset in days will be calculated for each type of event (first response or first remission) in person level. Participants who do not meet the criteria for respective type of event will be censored at the time of their last MADRS assessment during the treatment period.

For each type of event, the proportion of participants with onset of first events, Kaplan-Meier estimate in terms of the median time to onset of first event, and its 95% CI will be presented for each treatment group. Plots of the Kaplan-Meier estimate of the distribution of the time to onset of events will also be provided for each treatment arm. Log-rank tests comparing the time to onset of event distribution between each AGN-241751 dose and placebo will be conducted.

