16.0 DATA HANDLING CONVENTIONS

16.1 VISIT TIME WINDOWS

Table 16-1 presents the visits assigned for efficacy and safety analyses and the corresponding range of treatment days (window) during which an actual visit may occur.

Table 16-1 Visit Time Windows

Derived Visit	Scheduled Visit Day^a	Window
Baseline	Screening/Day 1 (Visit 2)	last nonmissing assessment before Index1 ^a
Day 2	Day 2 (Visit 3)	Days (Index1 ^a +1, IndexA ^b -1)
Day 8	Day 8 (Visit 4)	IndexA ^b
Day 9	Day 9 (Visit 5)	Days (IndexA ^b +1, IndexA ^b +4)
Day 15	Day 15 (Visit 6)	Days (IndexA ^b +5, day of final double blind visit or ET Visit occurring after IndexA ^b +5)
End of Double-Blind Treatment	The last available post-baseline assessment (unscheduled assessments) during the double-blind treatment period	
Safety Follow-up (Day 22)	Days [Day after final double-blind visit or ET visit occurring after Day 15 (Visit 6)/Early Termination visit]	

a Index1: Day of first double-blind dose

b IndexA: Day of second double-blind dose, if not received, use Index1 + 7 days

If the assessment date (if the assessment date is unavailable, use visit date instead) is on or after the date of the first dose of study treatment, the study day is calculated by assessment date – date of the first dose of study treatment + 1. If the assessment date is before the date of the first dose of study treatment, the study day is calculated by assessment date – date of the first dose of study treatment. Therefore, a negative day indicates a day before the start of the study treatment.

If a participant has 2 or more visits within the same window, the last visit with a nonmissing value will be used for analysis.

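### Part A time to first MADRS response or remission: dating events and censoring by assessment date lets the end of the Kaplan-Meier curve exceed the observed proportion and can print a late median where fewer than half responded

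*SAP*

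**What the plan says.** SAP 10.3 lists time to first response and time to first remission among the additional efficacy parameters. Time to onset "is defined as the number of days from the first randomized dosing to the first event". Participants who never meet the criterion "will be censored at the time of their last MADRS assessment during the treatment period". For each arm the "Kaplan-Meier estimate in terms of the median time to onset of first event, and its 95% CI will be presented", together with the crude proportion with onset, plots, and a log-rank test of each dose against placebo.

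Three other places decide what day is meant:

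- SAP 16.1 derives study day from calendar dates: for an assessment "on or after the date of the first dose of study treatment, the study day is calculated by assessment date" minus first-dose date, plus 1.
- Table 16-1 in the same section "presents the visits assigned for efficacy and safety analyses and the corresponding range of treatment days". It attaches visit labels. It does not say that event or censoring times are reset to the nominal day.
- SAP 4.0 allows that "study visits may be conducted up to 2 days before or after the scheduled visits". Only the pairs Visits 2/3 and 4/5 are fixed at 1 day apart, so Visit 6 can fall on Days 13 to 17.

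No interval-censored or discrete-time method is named. Protocol 10.3.1.3.1 has the same definitions for Part A.

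**The concern.** MADRS response can be observed only when a rating is made. In the Part A treatment period the scheduled post-dose ratings are at Visits 3, 4, 5 and 6. A completer who has not responded by Visit 5 has one more chance, at Visit 6, whichever day that visit falls on.

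If the calendar day is used, this single rating is spread over up to five days. A non-responder rated on Day 13 is censored on Day 13. A participant not rated until Day 17 stays in the risk sets of Days 13 to 16, when no event could be found in that person. Responders on the later days are therefore divided by a risk set that has already lost the early non-responders. The censoring belongs to the same visit as the events, so those still at risk do not stand in for those censored.

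At stake is a table that contradicts itself: a crude proportion, and beside it a curve and median that suggest more responders than were seen. A printed median would be read as half the arm having responded.

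**Working it through.** **Inputs from the documents.** About 25 participants per arm (SAP 14.0); nominal rating days 2, 8, 9 and 15; Visit 6 allowed on Days 13 to 17 (SAP 4.0). The documents give no response rate, median or visit-day distribution for this endpoint, so there is no planned figure to reproduce. Response rates, event timing and visit spread below are assumptions.

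**Formula.** S(t) = product over days d ≤ t of (1 − events on d / number at risk on d), with events counted before censorings on the same day. The Kaplan-Meier (KM) response is 1 − S at the end. The median is the first day on which S ≤ 0.5.

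**Worked examples.** 25 participants, no dropout, all first responses at Visit 6.

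| Visit 6 days | Seen per day | Responders per day | Crude | Final S | KM response |
|---|---|---|---|---|---|
| 13–17 | 5/5/5/5/5 | 1/1/1/1/1 | 5/25 = 20% | (24/25)(19/20)(14/15)(9/10)(4/5) = 0.613 | 38.7% |
| 13–17 | 2/3/15/3/2 | 0/1/3/1/0 | 5/25 = 20% | (22/23)(17/20)(4/5) = 0.650 | 35.0% |
| 14–16 | 5/15/5 | 2/6/2 | 10/25 = 40% | (23/25)(14/20)(3/5) = 0.386 | 61.4% |
| 15 only | 25 | 10 | 10/25 = 40% | 15/25 = 0.600 | 40.0% |

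The third row would print a median of Day 16 although 15 of 25 participants never responded. The fourth row holds the same 10 responders on the nominal day: KM equals the crude proportion and no median is reached. The first three rows are illustrations of the mechanism, not forecasts, because they put every event at Visit 6.

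**Where on the curve it occurs.** Without dropout nobody is censored before Visit 6, because non-responders at Visits 3, 4 and 5 stay at risk. With no censoring, KM equals the observed proportion. Under the ±2-day window the curve is therefore not inflated through Day 12, and simulation gives zero difference up to that day.

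**Simulation with events at all visits.** 25 per arm, 3,000 runs per scenario, no dropout; Visits 4 and 6 on schedule with probability 60%, and 10% on each other day of the window. First events not at Visit 6 are split 15:25:10 over Visits 3, 4 and 5.

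| Share of first events at Visit 6 | True 20% | True 30% | True 40% |
|---|---|---|---|
| 10% | 23% | 33% | 45% |
| 25% | 26% | 38% | 51% |
| 50% | 32% | 45% | 59% |
| 50%, but 95% of visits on schedule | 24% | 35% | 46% |
| Any share, nominal days | 20% | 30% | 40% |

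Repeat runs vary by 1 to 2 points.

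**Medians.** With half of first events at Visit 6 and 60% of visits on schedule, a median is printed in 15/36/62% of arms for true response of 20/30/40%, against 0/2/16% on nominal days. With a 10% share, a median appears although fewer than half responded in about 3/7/14% of arms.

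**Log-rank test.** With visit timing unrelated to arm, the null rejection rate is about 5% on either time scale. Power for 30% v 65% response at 25 per arm is about 65% on assessment dates and 70% on nominal days.

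**The case against.** The strongest reply is that the SAP never says that the actual day is used. A programmer who took nominal visit days would avoid the problem, and Table 16-1 does link ratings to visits. That stands as a caution. But counting days from dosing, censoring at the time of an assessment and deriving study day from dates all point the same way, and no text points to nominal days. The natural reading produces the bias, so the rule needs stating.

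A second reply is that the size is assumed. This also stands. Visits may move only if necessary. If few first events occur at Visit 6, or nearly all visits are on schedule, the excess is a few points.

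A third is that little depends on it. These are additional parameters without multiplicity control, in a sample not based on power, and the crude proportion and by-visit responder rates would expose the conflict. This limits the consequence; it does not make the curve or median right.

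The obvious remedy also has a trap. Under Table 16-1 the Day 2 window runs to the day before the second double-blind dose, so an early-termination response on Day 7 would be dated Day 2. If Visit 4 is on Day 10, the Day 9 window covers Days 11 to 14 and would capture a Visit 6 on Day 13 or 14. Dating by those windows would exchange one error for another.

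A reader might infer that the curves make onset look faster. They do not: Days 2 to 9 are unaffected without dropout, and a spurious median would be a late one.

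**Conclusion.** The point holds for Part A. Followed as written, the plan lets the end of each Kaplan-Meier curve, placebo included, exceed the observed proportion once Visit 6 falls on more than one day, non-responders are seen on an earlier day and a response is seen on a later one. It can print a median in an arm where most never responded. The direction follows from the rules. The size depends on visit-day spread, response rate and the share of first events at Visit 6: roughly 23/33/45% to 32/45/59% for true 20/30/40% when 60% of visits are on schedule, smaller when more are, and nil when all are.

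Stronger readings are not supported. A reader might infer a false claim of drug effect, but the log-rank level holds when visit timing is unrelated to arm, and the cost is about 5 points of power in the case above. The primary MMRM does not use these times. Nor can the Part B analysis be called wrong: its detail is left to a separate SAP that is not among the documents. It can only be noted that Protocol 10.3.1.3.2 repeats the censoring rule and that, for Visits 11 and 12, "these study visits may be conducted up to 1 day before or after the scheduled visit day". The change is worth making because a better rule is cheap.

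**What to change.** In SAP 10.3:

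- For ratings made at protocol-scheduled visits, set both event and censoring times to the nominal day of that visit (Days 2, 8, 9, 15). Use the scheduled-visit label, not the Table 16-1 window.
- Keep the actual day for early-termination and unscheduled ratings.
- Count events before censorings at ties.
- State that a Visit 6 on Day 16 or 17 belongs to the treatment period. SAP 4.0 ends that period at Day 15, while Table 16-1 runs to the final double-blind visit; read strictly, the former could send a late non-responder back to Visit 5 for censoring.
- Report the median as not reached when the visit-based curve stays above 50%.

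Alternatively, use an interval-censored (Turnbull) estimate with a matching test, which avoids the labelling question.

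The cost is a short addition to the text, a small programming change and up to 2 days of nominal time resolution, which a visit-based rating cannot support anyway. No new data are needed. The separate Part B SAP should adopt the same rule with its own visit days.
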